1.2.1.2 Clinical pharmacokinetics and pharmacodynamics

Ruxolitinib exhibits near complete oral absorption, achieving maximal plasma concentration Cmax at approximately 1-2 h post-dose with linear PK over a dose range of 5-200 mg. Ruxolitinib is mainly eliminated by metabolism via CYP3A4 with minor contributions of CYP2C9 with a terminal elimination half-life of approximately 3 h. Administration with food did not affect ruxolitinib's overall exposure. Ruxolitinib may be administered without regard to meals.

Ruxolitinib is metabolized in the liver by the cytochrome (CYP) P450 metabolizing enzyme system, predominantly by the 3A4 isozyme. The effects of the potent CYP3A4 inhibitor ketoconazole on the pharmacokinetics (PK) and pharmacodynamics (PD) of ruxolitinib administered as single oral doses shows that with concomitant dosing of ketoconazole, the observed AUC increase is approximately 2-fold, with a similar effect on the PD effect (cytokine-induced STAT3 phosphorylation). Thus, a dose reduction of approximately 50% for ruxolitinib is appropriate for subjects who take ketoconazole or other potent CYP3A4 inhibitors as concomitant medication.

Ruxolitinib was given as a single 25 mg dose to subjects with varying degrees of renal function ([INCB 18424-142]), including normal, mild, moderate and severe (ClCr < 30 mL/min) renal impairment as well as end stage renal impairment disease (ESRD). There was no statistically significant effect of mild, moderate or severe impairment of renal function on the PK or PD parameters; ESRD subjects requiring dialysis showed prolonged PD activity. In a hepatic impairment study, the PK of ruxolitinib was assessed following a single ruxolitinib dose of 25 mg [INCB 18424-137]. The mean AUC for ruxolitinib was increased by 87%, 28% and 65%, respectively, in subjects with mild, moderate and severe hepatic impairment compared to subjects with normal hepatic function, indicating no clear relationship to the degree of hepatic impairment based on Child-Pugh scores. The terminal elimination half-life was prolonged in subjects with hepatic impairment compared to healthy controls (4.1-5.1 h versus 3 h). Hepatic impairment, in general, decreased the plasma Cmax, but not the AUC

values, of ruxolitinib metabolites, and no rank correlation was observed between the change in the PK parameters of the metabolites and the degree of hepatic impairment.

The pharmacodynamics of ruxolitinib was characterized by an ex vivo whole-blood assay that involves quantification of phosphorylated STAT3 following IL-6 stimulation. Following single or multiple oral dose administrations, ruxolitinib demonstrated dose-dependent inhibition of cytokine-induced pSTAT3 with maximal inhibition occurring 1-2 h after administration. The pharmacodynamic-time profile (i.e., cytokine-induced pSTAT3 change over time) coincided with peak ruxolitinib plasma and trough concentrations. Additional details regarding the clinical pharmacology of ruxolitinib can be found in the IB.

1.2.1.3 Clinical experience

INCB 18424-256 is an uncontrolled open label dose-ranging Phase II study to determine the safety and efficacy of ruxolitinib in patients with advanced PV or ET refractory to or intolerant of HU. Following an initial 8-week phase in which three dose regimens (10 mg b.i.d., 25 mg b.i.d., or 50 mg q.d.) were evaluated in each patient population (n=6-8/dose), starting doses of 10 mg b.i.d. in PV patients and 25 mg b.i.d. in ET patients were selected, based on efficacy and tolerability, to explore in an expansion cohort. Dose modifications were allowed with the objective of normalizing hematocrit (Hct), platelet and WBC counts in each individual subject while avoiding hematologic toxicity. Primary endpoints include defined ranges for Hct, platelet and WBC counts for each disease; reduction in palpable spleen length; improvement in disease-related symptoms; reduction in the need for phlebotomy (PV only); and safety/tolerability. Thirty-four PV patients and 39 ET patients have been enrolled with a median time from diagnosis at study start of approximately 115 months for PV and 88 months for ET patients.

The first patient was enrolled in this study on 29-Aug-2008. The data were extracted from the clinical study report, 10-March-2011. The following information relates to the PV patients only.

1.2.1.3.1 Efficacy in INCB 18424-256

In total, 56% of PV subjects achieved an overall confirmed response after 8 weeks of ruxolitinib treatment (protocol-specified responder analyses). Unconfirmed response rates were higher, 62% in PV. These overall response rates were driven almost entirely by protocol-defined partial responses. Over the duration of the study, unconfirmed complete response was achieved with low frequency (18% PV), while partial response rates were achieved with greater frequency (91% PV).

Findings from specific and ad hoc analyses conducted for PV indicate normalization of Hct (<45%) was achieved rapidly with ruxolitinib and was sustained in all responding subjects in the absence of phlebotomy for the duration of their available follow-up. After 36 weeks of treatment, 97% of PV subjects achieved Hct control without the aid of phlebotomy and complete hematologic remission was achieved in 45% of subjects.

Within 12 weeks of treatment, 62% of PV subjects with splenomegaly at baseline achieved absence of palpable splenomegaly. Improvement of palpable splenomegaly, based on $\geq 50\%$ reduction from baseline in palpated spleen size was achieved in 81% of subjects after 36

weeks and was maintained in all responding subjects for the duration of their available follow-up. Enrolled patients demonstrated rapid, marked and durable reductions in patient-reported symptom scores for pruritus, night sweats and bone pain. These responses paralleled positive changes in the EORTC QLQ-C30 instrument.

1.2.1.3.2 Safety and tolerability in study INCB 18424-256

The overall risk-benefit of ruxolitinib in the PV population is favorable. The most frequently reported treatment emergent adverse events (TEAEs) were, respectively, anemia (73.5%), thrombocytopenia (32.4%), and diarrhea (20.6%). Of these most frequently reported TEAEs, relatively few were Grade 3 in severity: the percentage of subjects with Grade 3 anemia was 3%, Grade 3 thrombocytopenia 5.9% and no subject had Grade 3 diarrhea.

TEAEs in PV subjects were thrombocytopenia and pneumonia, each reported by two subjects (5.9%).

Few PV (2; 5.9%) subjects permanently discontinued study medication due to an AE. Few PV subjects (5; 14.7%) reported SAEs. Pneumonia was reported in two subjects with PV, and all other SAEs were reported only once (Verstovsek et al, 2014).

1.2.1.3.3 Phase III

The [\[CINC424B2301\]](#) study (RESPONSE Trial) is a global, randomized, open label pivotal study comparing ruxolitinib (starting dose of 10 mg b.i.d.) with BAT (Best Available Treatment: HU, pipobroman, immunomodulatory drugs, pegylated interferon or interferon, anagrelide, observation only) in PV patients. The protocol is designed for patients, either resistant or intolerant to HU, with evidence of need for phlebotomy for Hct control and presence of splenomegaly. The primary endpoint is a composite one with hematocrit control (Hct < 45% in the absence of phlebotomy from Week 8 to 32) and reduction in spleen volume by MRI (or CT if MRI is clinically contraindicated) of at least 35% measured at 32 weeks. Two key secondary endpoints include durability of the primary endpoint and complete hematologic remission. There are multiple, non-key secondary endpoints including modified clinico-hematologic response (overall response rate, durability and duration), as defined by the European Leukemia Net (ELN). Enrollment was completed in the study with 222 patients enrolled.

The trial met its primary endpoint.

The primary efficacy objective was based on a composite endpoint consisting of hematocrit control (absence of phlebotomy eligibility) and of at least 35% spleen volume reduction as assessed by central radiologic evaluation.

Significantly more patients randomized to ruxolitinib met the primary endpoint at Week 32 when compared to patients randomized to BAT, 22.7% vs. 0.9%, respectively ($p < 0.0001$).

Additionally at Week 32, a higher proportion of patients randomized to ruxolitinib achieved either of the individual components of the primary composite endpoint (95% CI are non-overlapping):

- 60.0% (95% CI: 50.2, 69.2) vs. 19.6% (95% CI: 12.7, 28.2) of the patients achieved hematocrit control (absence of phlebotomy eligibility) in the ruxolitinib arm vs. the BAT

arm, respectively. This difference was also reflected in the high proportion of patients randomized to ruxolitinib who had no phlebotomy from Week 8 to Week 32 (80.2%) when compared to patients randomized to BAT (37.6%)

- 40.0% (95% CI: 30.8, 49.8) vs. 0.9% (95% CI: 0.0, 4.9) of the patients achieved at least a 35% reduction in spleen volume from baseline in the ruxolitinib arm vs. the BAT arm, respectively.

Overall, 77.3% of the patients randomized to ruxolitinib met at least one component of the primary endpoint.

The safety profile of ruxolitinib was generally consistent with previous studies based on initial review of the data. .

[figure not shown]
2 Rationale

2.1 Study rationale and purpose

When cytoreduction is clinically indicated in PV patients, hydroxyurea (HU) is the preferred cytoreductive agent in the first line setting (Finazzi and Barbui 2007). However, HU treatment is associated with cytopenias and often unsatisfactory hematological control over time, aphthous and leg ulcers, multiple other toxicities, and a potential risk of leukemia estimated at up to 10% at the 13th year (Tefferi 2003, Najean 1997) For patients who do not tolerate or are resistant to HU, therapeutic options remain limited. The different available cytoreductive agents have been rarely compared in a randomized fashion and their use is supported by little prospective evidence. The most commonly used second-line therapies include pipobroman, anagrelide, Peginterferon/interferon alpha, ³²P and alkylating agents (Marchioli 2005). Imids have shown clinical activity in the MPDs, most specifically in Primary Myelofibrosis and post-ET/PV myelofibrosis (Barosi 2001).

Ruxolitinib is an inhibitor of the Janus kinase family of protein tyrosine kinases (JAKs) that is currently under development for treatment of myeloproliferative neoplasms (MPNs) and advanced hematologic malignancies. A causal role for JAK2 has recently been proposed for PV patients possess the JAK2 V617F mutation. As described in [Section 1.2](#), data from the Phase II Study (INC 18424-256) in PV patients refractory or intolerant to HU have demonstrated that treatment with ruxolitinib is effective and well tolerated, and can result in normalization of Hct, white blood cell count, and platelet count while eliminating the need for phlebotomy. When present, splenomegaly is markedly improved by ruxolitinib treatment as evidenced by the rapid and durable decreases in palpable spleen length with therapy. The symptomatic burden of enrolled patients, namely pruritus, bone pain, fever and night sweats, are improved by ruxolitinib as reported by patient-reported symptom assessments.

In addition, a global phase III CINC424B2301 study (RESPONSE Trial), randomized, open label comparing ruxolitinib (starting dose of 10 mg b.i.d.) with BAT in PV patients either resistant or intolerant to HU, with evidence of need for phlebotomy for Hct control and presence of splenomegaly has met its primary endpoint. The safety profile of ruxolitinib was generally consistent with previous studies based on initial review of the data. The results of this trial have been submitted to the upcoming ASCO and EHA 2014 meetings. Taken together,

the emerging efficacy and safety profile for ruxolitinib supports further access in PV patients who demonstrate resistance or intolerance to HU therapy.

2.2 Rationale for the study design

2.3 Rationale for dose and regimen selection

The purpose of this open-label, single arm, multi-center Expanded Treatment Protocol (ETP) is to provide early access to ruxolitinib and evaluate safety information in patients with PV, who are HU resistant or intolerant and who have no other standard treatment option, nor do they qualify for another clinical study for PV.

The available data from Study INCB 18424-256 established 10 mg bid starting dose of ruxolitinib as an active, safe and well tolerated dose in patients with PV. Primary endpoints include defined ranges for Hct, platelet and WBC counts; reduction in palpable spleen length; improvement in disease-related symptoms; reduction in the need for phlebotomy; and safety/tolerability. Thirty-four PV patients were enrolled. [Section 1.2.1.3](#) provides more information on the safety and efficacy results from this study that support the use of a 10 mg bid starting dose in the PV patient population.

In this study, all patients will be initiated at a dose of 10 mg bid (see [Section 6.3.4](#) and [Section 6.3.7](#) for exceptions). Dose levels of ruxolitinib will be adjusted based on safety and efficacy so that each patient is titrated to their optimal dose, and the starting ruxolitinib dose will likely not be the final dose for many patients. In addition, the global phase III ([\[CINC424B2301\]](#) or the RESPONSE Trial) confirmed that a starting dose of 10 mg b.i.d. is an active and well tolerated dose.

The highest ruxolitinib dose allowed in study INCB 18424-256 and CINC424B2301 was 25 mg bid. This dose has been established as the maximally tolerated dose in healthy volunteers, and has been safe and well tolerated in MF and PV when the dose level has been implemented as part of individualized dose titration.

See the IB for more information on ruxolitinib PV clinical study findings.

2.4 Rationale for choice of combination drugs

Not applicable.

2.5 Rationale for choice of comparators drugs

Not applicable.

3 Objectives and endpoints

Objectives and related endpoints are described in Table 3-1 below.

Table 3-1 Objectives and related endpoints

| Objective | Endpoint | Analysis |
|---|---|---|
| Primary | | Refer to Section 10.4 |
| To evaluate the safety of ruxolitinib | AEs, Grade 3&4 AEs & SAEs, events of special interest, AEs leading to discontinuation, and deaths. Evaluate changes in hematology." | |
| Secondary | | |
| Efficacy | Change in Hct levels from Baseline to each visit where measured | Refer to Section 10.5.2 |
| To evaluate change in hematocrit levels | Change in spleen length from Baseline to each visit where measured. | |
| Patient Reported Outcome | Change in MPN-SAF TSS score from baseline to each visit where measured. | Refer to Section 10.5.6 |
| To evaluate change in MPN-SAF TSS score | | |

4 Study design

4.1 Description of study design

This is a global, single arm, open-label, multi-center protocol designed to provide early access and evaluate the safety of ruxolitinib in patients with polycythemia vera who are HU resistant or intolerant and who have no other standard treatment options. Efficacy and patient reported outcomes will also be assessed.

There are limited therapeutic options in this disease setting. Ruxolitinib will be provided until it becomes commercially available for this indication in each participating country or until 31 December 2017, whichever date occurs first.

Screening/baseline phase

- Screening/baseline assessments will be performed within 35 days prior to the first dose of ruxolitinib treatment (e.g., labs including hematology, blood chemistry, urine, and pregnancy tests, physical examination including spleen palpation, vital signs, and ECOG Performance Status).
- If all screening lab assessments are received, reviewed, and within protocol parameters and patient meets all inclusion and none of the exclusion criteria, the screening labs may be used as baseline and patient may continue to Day 1 within 14 days of the screen after the eligibility checklist has been completed in the IRT system.

Treatment phase/duration of treatment

- Patients who are eligible will receive ruxolitinib at a starting dose of 10 mg bid (see [Sections 6.3.4](#) and [Section 6.3.7](#) for exceptions). The first dose of ruxolitinib treatment is

administered on Day 1. Patients will have clinic visits every 4 weeks until Week 24 and every 12 weeks thereafter. The dose of drug may be adjusted during the study based on efficacy and safety to a maximum of 25mg bid (see [Sections 6.3](#) for guidance). Clinical suspicion of disease progression to MF, MDS, or AML (see [Appendix 4](#) and [Appendix 5](#) for definitions) or the occurrence of a Grade 3 or 4 events at any time requires a physical examination to assess disease status. This examination is to be performed promptly rather than waiting for the next scheduled visit.

- Patients may continue to receive ruxolitinib treatment until disease progression, (see [Appendix 4](#) and [Appendix 5](#)), as determined by the local investigator, unacceptable toxicity, death, withdrawal of consent for protocol specified procedures, or discontinuation from the treatment for any other reason until the drug becomes commercially available in each participating country or until 31 December 2017, whichever occurs first.

4.2 Timing of interim analyses and design adaptations

Not applicable.

4.3 Definition of end of the study

The study will end for each country 3 months after the drug is commercially available in the country or by 31 December 2017, whichever occurs first. The entire study will end when all countries have completed participation.

Should ruxolitinib not be available to patients after the drug is commercially available in the country, Novartis Country Pharma Organization will have a transition plan in place to ensure that patients have access without delays in treatment.

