6.1.5 Treatment duration

Patients may continue ruxolitinib treatment until they experience any of the following:

- Disease progression determined by the local investigator (see [Appendix 4](#) and [Appendix 5](#)),
- Unacceptable toxicity that precludes further treatment,
- Start of a new anti-cancer therapy,
- Pregnancy,
- Treatment is discontinued at the discretion of the investigator or patient,
- Lost to follow-up or withdrawn consent,
- Death,
- Study terminated by the sponsor,
- Study is completed (see definition below).

Treatment duration is considered “completed” three months after ruxolitinib becomes commercially available in the patients participating country or by 31 December 2017, whichever comes first, and the patient should be transitioned to commercial product. Study sites should stop all patients’ study participation on the ETP at this time.

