7.1.3.1 Criteria for premature patient withdrawal

Patients may voluntarily withdraw from the ETP at any time.

Patient death will be considered as a withdrawal from the study. Patients may also be withdrawn (the physician may decide to remove the patient from any further study activity) if any of the following occur:

- Adverse event(s) (see [Section 8.1](#))
- Major protocol deviation
- Technical problems
- Physician decision
- Non-compliance with study treatment

Patients must be withdrawn if any of the following occur:

- Lost to follow-up
- Patient/guardian decision
- Study terminated by sponsor
- Pregnancy (Pregnancy will be followed for outcome)
- Disease progression – sites should indicate type of progression and include information on the diagnostic bone marrow biopsy result if obtained as per diagnostic criteria (see [Appendix 4](#) and [Appendix 5](#)).
- Withdrawal of consent

Patients lost to follow up should be recorded as such on the eCRF. For patients who are lost to follow-up, the investigator should show "due diligence" by documenting in the source documents steps taken to contact the patient, e.g. dates of telephone calls, registered letters, etc.

Treatment duration is considered "completed" three months after the expanded treatment plan's drug becomes commercially available for the PV indication in the patients participating country or by 31 Dec 2017, whichever comes first, and the patient should be transitioned to commercial product. Study sites should stop all patients' study participation on the study at this time.

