7.1.4 Follow up period

All patients must have a follow up safety phone evaluation 30 days after the last dose of treatment (Study Evaluation Completion or EoS).

Patients lost to follow up should be recorded as such on the CRF. For patients who are lost to follow-up, the investigator should show "due diligence" by documenting in the source documents steps taken to contact the patient, e.g., dates of telephone calls, registered letters, etc.

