10.5.3 Safety objectives

10.5.3.1 Analysis set and grouping for the analyses

For all safety analyses, the safety set will be used.

The overall observation period will be divided into mutually exclusive segments:

1. pre-treatment period: from day of patient's informed consent to the day before first dose of study medication
2. on-treatment period: from day of first dose of study medication to 30 days after last dose of study medication
3. If applicable, post-treatment period: starting at day 31 after last dose of study medication.

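### Study closure and the stop-participation instruction can fall on the day of last dose, which conflicts with the mandatory 30-day safety contact

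*Protocol*

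**What the plan says.** **Closure.** Protocol 4.3 sets the country-level end: "The study will end for each country 3 months after the drug is commercially available in the country or by 31 December 2017", whichever is earlier. For the trial as a whole it adds only "The entire study will end when all countries have completed participation". No follow-up period is attached to either statement.

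**End of treatment.** Protocol 6.1.5 regards treatment as complete "three months after ruxolitinib becomes commercially available in the patients participating country or by 31 December 2017", again the earlier of the two. It then directs sites to halt all patients' "study participation on the ETP at this time". Section 7.1.3.1 gives the same rule and the same direction ("study participation on the study at this time"). Section 4.1 differs on one route. It lets treatment run until the drug is "commercially available in each participating country or until 31 December 2017, whichever occurs first", with no extra three months after launch.

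**Follow-up.** Protocol 7.1.4 states: "All patients must have a follow up safety phone evaluation 30 days after the last dose of treatment". It labels that contact as study evaluation completion, or end of study. Section 7.1.3 makes a day-30 telephone contact the minimum for everyone who stops treatment. Section 8.1.1 asks for AE monitoring, and 8.2.2 for SAE reporting, over at least 30 days after treatment.

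**Analysis.** Protocol 10.5.3.1, repeated in SAP 2.8, defines the "on-treatment period: from day of first dose of study medication to 30 days after last dose of study medication". Protocol Section 10 and SAP 2.1 make the final analysis wait until all patients, including those who complete treatment per protocol, have had 30 days of follow-up.

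**The concern.** Two sets of instructions cannot both be followed for a patient who takes drug up to the closing date. One set closes the country and ends participation that day. The other requires a contact, AE monitoring and SAE reporting over the next 30 days.

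Safety is the primary objective, and treatment-emergent AEs are tabulated over a window that includes those 30 days. If a site gave priority to the closing instruction, completers would have on-treatment time with no planned contact, while patients who stopped earlier would have had theirs. Protocol 10.4.3 applies no imputation for missing data, so events not collected then would simply be absent from the tables.

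**Working it through.** The plan gives no figure to reproduce. The check is calendar arithmetic on its own dates, followed by a search for any passage that removes the conflict.

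**Inputs**
- E, study end in a country: the earlier of launch + 3 months and 31 December 2017 (Protocol 4.3).
- T, last permitted treatment date. Under 6.1.5 and 7.1.3.1 it is the earlier of launch + 3 months and 31 December 2017. Under 4.1 it is the earlier of launch and 31 December 2017.
- C, contact date: last dose + 30 days (7.1.3, 7.1.4).

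**Formula.** With last dose on T, the contact falls C − E = 30 − (E − T) days after closure. A negative result means that it falls before closure.

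| Route | E − T | C − E |
|---|---|---|
| 31 December 2017 limit (4.1, 6.1.5, 7.1.3.1) | 0 days | 30 − 0 = 30 days after closure, on 30 January 2018 |
| Launch route, 6.1.5 and 7.1.3.1 | 0 days | 30 − 0 = 30 days after closure |
| Launch route, 4.1, full three months available (launch by 30 September 2017) | 89 to 92 days | 30 − 89 = −59 to 30 − 92 = −62, so before closure |
| Launch route, 4.1, launch on 1 December 2017 | 30 days | 0, on the closing day |
| Launch route, 4.1, launch on or after 2 December 2017 | 29 days or fewer | at least 1 day after closure |

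**Does the word *by* help?** For the contact to fall on or before 31 December 2017, the last dose could be no later than 31 December − 30 days = 1 December 2017. The wording permits that, but no passage requires it.

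**Does the half-life alternative in 8.1.1 shorten the window?** Section 1.2.1.2 gives a half-life of about 3 h, and up to 5.1 h with hepatic impairment. Five half-lives are 5 × 3 = 15 h to 5 × 5.1 = 25.5 h. The longer period applies, so 30 days governs.

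**Does a definition cure it?** The glossary ends participation at whichever comes later, attendance at a closing evaluation or the stop of study drug. A telephone contact is neither. Section 7.1.3 regards patients as withdrawn once the final visit assessments are done. Neither passage carries participation through to day 30.

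**What does the rest of the protocol assume?** Exclusion criterion 18 treats the 30-day safety follow-up as part of study duration, and 7.1.4 calls the contact the end of study. Against these, 4.3 and the stop instructions are the outliers.

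**The case against.** The best counter-argument is that the follow-up is not missing. It is required of all patients in 7.1.4, repeated in 7.1.3, and assumed by 8.1.1, 8.2.2 and Section 10. On that view a patient-level requirement is not cancelled by a country-level administrative date, and a site that skipped the contact would breach the protocol. This stands in part. It means that loss of data cannot be presumed. It does not make the instructions consistent, because 6.1.5 and 7.1.3.1 are also addressed to sites, concern individual patients' participation, and take effect on the treatment-end date.

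A second argument is that 4.1 leaves about three months between end of supply at launch and study end. This is correct for that route, except for launches on or after 2 December 2017. A reader might infer that closure leaves no room for follow-up whichever treatment-end date governs, and 4.1 shows that this is too broad. The 31 December 2017 route does not depend on the discrepancy between 4.1 and 6.1.5/7.1.3.1. The launch route does.

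Third, completers are meant to move to commercial drug, and 4.3 promises a transition plan without treatment delays. A reader might infer that withdrawal events of the kind 6.3.8 anticipates would go uncollected in completers. As planned, most would change supply and not stop the drug, so that inference is weak. Section 6.3.8 itself also keeps the 30-day contact.

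The body of Table 7-1 was not available for this check. If it schedules the contact, it adds another passage that requires it, but it would not alter 4.3 or the stop instructions.

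**Conclusion.** The conflict is real and should be corrected. The closing date in 4.3 and the stop instructions in 6.1.5 and 7.1.3.1 allow zero days between last dose and closure. This holds on the 31 December 2017 route under each passage that states that limit, and on the launch route under 6.1.5 and 7.1.3.1. In those cases all 30 follow-up days lie after formal closure. Under the launch wording of 4.1 the contact usually fits.

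The consequence is contradictory instructions and a risk of incomplete AE collection in completers, in time that the primary safety analysis counts as on-treatment. Two stronger conclusions might be drawn, and the documents support neither:
- A reader might infer that completers will not be followed, or that their non-serious AEs have no collection route. Section 8.1.1 requires monitoring of all AEs for at least 30 days, and 7.1.4 supplies the contact.
- A reader might infer a known understatement of AEs in the largest group of patients. The documents do not say how many of the approximately 500 patients would complete, so neither the share affected nor the size of any bias can be given.

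The 30-day figure assumes that dosing runs to the last permitted date. An earlier last dose shortens the gap day for day.

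**What to change.** - **Protocol 4.3:** define the end of study in each country as the date on which the last patient there has had the 30-day safety evaluation after last dose.
- **Protocol 6.1.5 and 7.1.3.1:** state that participation ends after the 7.1.4 evaluation.

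The treatment-end dates in 4.1 and in 6.1.5/7.1.3.1 also differ, and the sponsor must reconcile them separately. The wording above works with either date and does not choose between them.

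**Cost:** an amendment touching three sections, with site and database close-out about 30 days later. No visit or procedure is added, because the contact is already required. The final analysis need not move, because Section 10 already waits for the same 30 days.
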